3. SUMMARY OF STUDY PLAN

This is an open-label, randomized, cross-over study, evaluating whether two different doses of Avmacol® (4 tablets per day for 10-14 days; 8 tablets per day for 10-14 days) increase the detoxification of tobacco carcinogens in otherwise healthy, current heavy smokers. Participants will serve as their own controls. We chose the open-label design because the study endpoints are not likely to be affected by the knowledge of the dosage assignment. We believe that the proposed randomized cross-over design would minimize the potential bias from the open-label design. We plan to accrue 61

eligible participants to initiate agent intervention. With an anticipated attrition rate of 33% or less (with respect to completing the intervention and having complete endpoint data), we expect to have at least 41 participants with evaluable endpoint data. Projected accrual is 2 participants per month.

Participants will undergo a screening evaluation (Visit 1) in which the informed consent form will be signed. Participants will be assessed for study eligibility. Detailed inclusion and exclusion criteria are listed in sections 4.1 and 4.2. All participants will undergo evaluation to obtain height, weight, blood pressure, pulse, temperature measurements, a brief physical exam consisting of an examination of the heart, lungs and abdomen, and Karnofsky performance status assessment. They will also be evaluated for concurrent medication and supplement use, baseline tobacco/alcohol assessment, medical history, and laboratory analysis with complete blood count with differential (CBC-diff), comprehensive metabolic panel (CMP). Women of childbearing capacity will have a urine pregnancy test. Study participants will be provided with a daily diary for recording any adverse events (AEs) and medication usage and a urine collection kit (an overnight urine collection container, a collection hat, and instructions for collecting overnight urine) to be used the night prior to Visit 2.

Once determined eligible, participants will be randomized (1:1) to one of the following arms: High-Low Arm (8 tablets Avmacol® per day during Intervention Period 1 and 4 tablets Avmacol® per day during Intervention Period 2) and Low-High Arm (4 tablets Avmacol® per day during Intervention period 1 and 8 tablets Avmacol® per day during Intervention Period 2).

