Participants will return to the clinic for Baseline Specimen Collection for Intervention Period 1 (Visit 2). Participants will be contacted prior to the visit to remind them to collect overnight urine the night prior to Visit 2. Participants will bring the overnight urine to the clinic and undergo baseline specimen collection for the collection of buccal cells (for NRF target gene transcripts), nasal brushing (banked for gene expression analysis) and blood (for genotyping and banking). Participants will be assessed for baseline symptoms, concomitant medications, and be queried on current tobacco use. Urine pregnancy test will be repeated, if applicable. Those who miss the overnight urine collection prior to Visit 2 will be asked to collect overnight urine the night of the visit and return the urine to the clinic the following day. Participants will be provided with Avmacol® pills for Intervention Period 1 after confirmation of overnight urine collection. Participants will be provided with an Intake Calendar for recording agent intake.

During Intervention Period 1 (10-14 days), participants in the High-Low Arm will take 8 tablets of Avmacol® each day and participants in the Low-High Arm will take 4 tablets of Avmacol each day. Participants will be instructed to take the Avmacol® pills with the evening meal. Day 1 of the Intervention Period 1 begins the day the first dose is taken. During Intervention Period 1, participants will return to the clinic on Day 4, 5, 6, 7, or 8 for an Interim Visit (Visit 3). Participants will undergo the collection of buccal cells and be assessed for AEs, concomitant medications and be queried on current tobacco use. Participants will be provided with a new urine collection kit to be used the night prior to Visit 4.

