Participants will return to the clinic at the end of Intervention Period 1 (Visit 4). Participants will be contacted prior to this visit to remind them to collect overnight urine the night prior to Visit 4. Participants will bring the overnight urine to clinic, return unused pills, undergo specimen collection for the collection of buccal cells, nasal brushing and blood. Participants will also be assessed for AEs, concomitant medications, compliance, and be queried on current tobacco use. Those who miss the overnight urine collection prior to Visit 4 will be provided with additional Avmacol® pills and be asked to take the pills the evening of Visit 4 and collect overnight urine the night of the visit and return the urine to the clinic the following day. Participants will be provided with a new urine collection kit to be used the night prior to Visit 5.

Participants will undergo a Washout Period (10-14 days) after completing Intervention Period 1. After the Washout Period, participants will return to the clinic (Visit 5) to undergo baseline specimen collection for Intervention Period 2. Participants will be contacted prior to the visit to remind them to collect overnight urine the night prior to Visit 5. Participants will bring the overnight urine to the clinic and undergo baseline specimen collection for the collection of buccal cells, nasal brushing and blood. Participants will also be assessed for AEs, concomitant medications, and be queried on current tobacco use. Urine pregnancy test will be repeated, if applicable. Those who miss the overnight urine

collection prior to Visit 5 will be asked to collect overnight urine the night of the visit and return the urine to the clinic the following day. Participants will receive Avmacol® pills for Intervention Period 2 after the overnight urine collection is confirmed.

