5.2 Avmacol® Administration

- Participants will receive a supply of Avmacol® for each Intervention Period upon confirmation of overnight baseline urine collection.
- Participants will be instructed to take the assigned Avamacol pills (4 or 8) with the evening meal.

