Zhang et al. treated female Sprague-Dawley rats with BSP to study the effect on tissue GST and NQO1 and the urinary excretion levels of isothiocyanate (ITC) metabolites. These experiments included administration of BSP providing 40, 80, and 160 µmol isothiocyanate/kg body weight daily for 14 Days. None of the extract doses were associated with any sign of toxicity, with all rats in good health and body weight gain not significantly different among treatment and control groups. No gross abnormalities were detected at necropsy. No pathological changes were visible in rat bladder tissues when examined microscopically. BSP in the doses administered effectively induced GST and NQO1 enzyme expression in rat bladder, duodenum, and stomach in a dose-dependent fashion. Significant enzyme expression was induced in rat colon, kidney, and lungs at the higher dose of broccoli seed extract. Measurement of urinary ITC and metabolites by cyclocondensation assay showed extensive (70-78%) elimination of the ITC doses within 24 hours. ITCs are known to be metabolized in vivo mainly through the mercapturic acid pathway and to be excreted in the urine as NAC conjugates (55).

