8.2 Secondary Endpoints

The secondary endpoints are:

- To determine the changes (from baseline to end-of-intervention for each Intervention Period) in the urinary excretion of the mercapturic acids of acrolein and crotonaldehyde after Avmacol® intervention. Similarly, the urinary biomarkers will be normalized by the urinary creatinine levels. The changes following 4 tablets of Avmacol® per day and after 8 tablets of Avmacol® per day will be calculated separately for each tobacco carcinogen.
- To determine whether Avmacol® increases the urinary excretion of the mercapturic acids of tobacco carcinogens, normalized by bio-measurement of tobacco exposure. Bio-measurement of tobacco exposure will be assessed by the total urinary levels of nicotine and major nicotine metabolites (i.e., the sum of the molar concentrations of nicotine and major nicotine metabolites in urine). The changes following 4 tablets of Avmacol® per day and after 8 tablets of Avmacol® per day will be calculated separately for each tobacco carcinogen.
- To determine the changes (from baseline to day 4-8 and to end-of-intervention) in the NRF2 target gene transcripts, assessed by the expression of *NQO1*, in the buccal cells after Avmacol® intervention. The changes following 4 tablets of Avmacol® per day and after 8 tablets of Avmacol® per day will be determined separately.
- To determine whether there is a dose-response relationship between the Avmacol® dose and the detoxification of tobacco carcinogens and the change in the NRF2 target gene transcripts.
- To determine the relationship between systemic study agent exposure, assessed by the total urinary levels of sulforaphane and its glutathione-derived metabolites (i.e., the sum of the molar concentrations of sulforaphane and its glutathione-derived metabolites in urine), and changes in detoxification of tobacco carcinogens and NRF2 target gene transcripts.

The study also includes the following explorative endpoints:

- To determine whether the *GSTM1* and *GSTT1* genotypes are important genetic modulators of detoxification of tobacco carcinogens. The change in the urinary excretion of the mercaptoruinc acids of tobacco carcinogens will be compared between *GSTM1*-null and *GSTM1*-positive subjects and between *GSTT1*-null and *GSTT1*-positive subjects.
- To bank specimens for future research including tobacco gene signature in nasal brushing, and fixed buccal cells for nuclear morphometry.

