10.2 Collection and Handling Procedures

Blood for clinical chemistry, hematology and coagulation panels

Twelve and a half milliliters of blood (1 x 8.5 ml SST tube; 1 x 4 ml Lavender-EDTA tube) will be collected at screening and at the end of intervention for CBC with diff and CMP. The SST tube will be held at room temperature for 30 min and then centrifuged. The lavender EDTA tube will be gently inverted to mix for anticoagulation. Blood tubes will be prepped, labeled, and packaged according to the recommendation from the diagnostic laboratory. All samples will be refrigerated prior to transfer to the commercial laboratory and sent for immediate analysis.

Urine for pregnancy test

A single void urine will be collected and tested for pregnancy in the clinic according to package instructions.

Overnight urine collection

Overnight urine will be collected the night prior to Visits 2, 4, 5, 7. Participants will record the start and stop time of urine collection on a designated collection form and will bring overnight urine collections to research visits. If urine collection was not done the night prior to the visit, overnight urine may be collected the night of the visit. The volume of urine collected from each overnight void will be recorded by study staff to the nearest 10 mL. Five 5 mL aliquots of urine will be retained for testing and the remaining urine discarded. The sample tubes will be labeled with the study ID, participant ID, and visit number/date and stored at -70° or below until analysis.

Buccal cell collection

Buccal cells will be collected at Visits 2, 3, 4, 5, 6, 7. As described, the buccal cells will be collected in two forms: 1) into a cryovial preserved in RNALater upon collection (the first 3 brushes); 2) fixed onto 3 glass slides for nuclear morphometry (the fourth brush). Cryovial specimens will be labeled with the study ID, participant ID, and visit number/date and stored at -70° or below until analysis. Buccal cell glass slides will also be labeled with the study ID, participant ID, and visit number/date. After the buccal cell glass slides are collected, the slides are allowed to dry at room temperature for about 30 minutes. Buccal cell slides are then fixed for 10 minutes in room temperature 10% neutral buffered formalin (using a coplin jar). Slides can then be dried for as long as overnight at room temperature in a slide rack. Slides will then be stored in a labeled slide box stored at room temperature.

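### Urinary sulforaphane exposure is an unadjusted concentration with no recorded dose time, which adds avoidable error to one secondary correlation

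*Combined protocol and SAP*

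**What the plan says.** - **Dose.** Section 5.2: "Participants will be instructed to take the assigned Avamacol pills (4 or 8) with the evening meal". No clock time is set. Section 3 adds: "Participants will be provided with an Intake Calendar for recording agent intake". Whether that calendar has a field for the time of day is not stated.
- **Urine.** Section 10.2 schedules overnight collections before Visits 2, 4, 5 and 7, and says "Participants will record the start and stop time of urine collection on a designated collection form" and "The volume of urine collected from each overnight void will be recorded by study staff to the nearest 10 mL". It does not define overnight or say when collection begins relative to the dose.
- **Link between the two.** The make-up rule in Section 3 tells participants to "take the pills the evening of Visit 4 and collect overnight urine the night of the visit", so at the end of each intervention period urine is meant to follow a dose taken the same evening. The kit contains "instructions for collecting overnight urine", which are not reproduced in the document.
- **Exposure measure.** Section 8.2: "To determine the relationship between systemic study agent exposure, assessed by the total urinary levels of sulforaphane and its glutathione-derived metabolites", computed by adding molar concentrations. No volume, duration, creatinine or time-since-dose term is given for this measure. By contrast, Section 8.1 normalises the primary benzene marker by creatinine.
- **Use.** Section 13.5 correlates exposure with biomarker change by Spearman coefficient. Section 5.7.2 allows urinary sulforaphane as a further check on compliance.

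**The concern.** Sulforaphane and its metabolites passed between the meal and the start of collection are not in the sample. The share missed depends on the gap between dose and start, which varies with meal and bedtime habits. Without the dose time that gap is unknown and cannot be modelled later. Separately, a raw concentration depends on how dilute the urine is, yet the volume and times recorded under Section 10.2 are left out of the definition in Section 8.2.

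At stake is the secondary objective relating systemic exposure to biomarker modulation. Error of this kind pulls a rank correlation toward zero, so a real relationship could be missed in a sample of about 41.

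**Working it through.** **The plan's own figure.** The only stated power is for the primary paired t test (Section 13.4): N = 41, two-sided alpha 0.025, effect 0.50 SD. The noncentral t distribution gives 80.5%, so the stated figure of at least 80% reproduces, and 61 × 0.67 = 40.9, about 41. None of this depends on the exposure measure. No power is stated for the Spearman analysis.

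**Effect of the gap.** The only excretion-time figure is for rats (Section 6.2.1): "extensive (70-78%) elimination of the ITC doses within 24 hours". Its midpoint, 74%, leaves 26% at 24 h, so the implied half-life is 24 × ln 2 / −ln 0.26 ≈ 12.3 h. Half-lives of 2.5 h and 4 h are assumed as faster cases. Also assumed: first-order excretion from the dose, and collection ending 12 h after it.

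Fraction captured = exp(−k·start) − exp(−k·12), with k = ln 2 / half-life. For 4 h: start at 1 h gives 0.841 − 0.125 = 0.716; start at 5 h gives 0.420 − 0.125 = 0.295. The amount ratio is 0.716 / 0.295 = 2.4. The rate ratio is (0.716 / 11) / (0.295 / 7) = 1.5.

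Rank correlation with true exposure was simulated (200,000 draws, log-exposure SD 0.4, start uniform over 1–5 h).

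| Half-life | Captured, start 1 h | Captured, start 5 h | Ratio, amount | Ratio, rate | Rank corr., amount | Rank corr., rate |
|---|---|---|---|---|---|---|
| 2.5 h | 0.722 | 0.214 | 3.4 | 2.1 | 0.72 | 0.86 |
| 4 h | 0.716 | 0.295 | 2.4 | 1.5 | 0.82 | 0.95 |
| 12.3 h | 0.437 | 0.246 | 1.8 | 1.1 | 0.92 | 0.996 |

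A pooled concentration is amount divided by volume. If volume grows with duration, its timing error follows the rate columns, and urine flow adds dilution error on top.

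**Effect on the correlation.** In the same simulation a true Spearman of about 0.38 becomes about 0.28 to 0.35 on amount and 0.33 to 0.38 on rate. With a raw concentration, an assumed urine-volume CV of 50% and no timing gap, it falls to about 0.24. Dilution therefore costs more than timing.

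**Sensitivity to the spread of true exposure.** A second model adds absorption (half-lives 2–6 h, gap 1–5 h, stop at 10–14 h). Rank correlation of amount with true exposure:

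| True exposure | Rank correlation |
|---|---|
| Uniform over 1–40% (Section 6.2, oral glucoraphanin) | 0.85–0.94 |
| CV 50% | 0.76–0.90 |
| CV 30% | 0.58–0.79 |
| Confined to 60–80% (Section 6.2, sulforaphane-rich extract) | 0.21–0.35 |

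At CV 50%, raw concentration gives about 0.69 with no gap and 0.60–0.65 with it.

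**Effect on power.** Fisher z with SE = √[(1 + ρ²/2) / (n − 3)], n = 41, two-sided 0.05. For ρ = 0.45: z = 0.485, SE = 0.170, power about 81%. At a half-life of 3 h and CV 50%, the rank correlation of amount is 0.84 for a 1–5 h gap and 0.73 for a 0–6 h gap. Then 0.45 × 0.84 = 0.38, power about 66%, and 0.45 × 0.73 = 0.33, power about 53%.

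**The case against.** The strongest reply is that little is lost. Section 8.2 uses a concentration, so the rate figures are the relevant ones for timing. At the one half-life derived from the document (rats, 12.3 h) the timing loss on that scale is nil. With 41 participants the standard error of a Spearman near 0.38 is roughly 0.14, larger than the timing loss on the rate scale. This stands as to size, and it is why the point is small. It does not answer the dilution error.

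It may also be said that creatinine correction is implied, since the first item of Section 8.2 normalises urinary biomarkers that way. That sentence sits in the item on acrolein and crotonaldehyde. The exposure item gives its own formula without it.

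The unseen kit instructions may fix the start relative to the dose, and the Intake Calendar may hold dose times. Either is possible. If the start is fixed, only the concentration definition remains at issue.

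A reader might infer more than the document supports:

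- *That the measure cannot rank exposure.* Rank correlation stays at 0.72–0.92 on amount and 0.86–0.996 on rate. It comes close to lost only in the 60–80% case, which Section 6.2 gives for sulforaphane-rich extract, not for Avmacol.
- *That the two-fold dose step is hidden in the dose-response analysis.* Section 13.5 models dose-response on Avmacol dose, not urinary sulforaphane, and each participant takes both doses.
- *That compliance is undermined.* Sections 5.7.1 and 13.6 define compliance for analysis by pill count; urine is an optional extra.

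**Conclusion.** The point holds as a cheap improvement to one unpowered secondary analysis. As defined, the exposure measure ignores dilution, collection duration and time since dose, and the dose time needed to correct for the last of these is not required anywhere in the protocol. For the same true exposure, a 1 h versus 5 h gap shifts the value by about 1.1- to 2.1-fold (rate) or 1.8- to 3.4-fold (amount), and unadjusted dilution adds more. The Spearman correlation is attenuated and ranking is degraded, not abolished. The primary benzene endpoint, its power and the dose-response models are untouched.

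These sizes rest on assumed human kinetics, assumed gaps of 1–5 h, an assumed spread of exposure and an assumed urine-volume CV of 50%. That the definition omits the recorded volume and times rests on the text alone.

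**What to change.** 1. **Section 10.2 and the collection form:** at Visits 4 and 7, record the clock time of that evening's dose.
2. **Sections 8.2 and 13.5:** define exposure either as amount excreted over the recorded interval (concentration × total recorded volume) or as a creatinine-normalised value, and choose one in advance.
3. **Section 13.5:** adjust the exposure-biomarker correlation for the dose-to-start gap and collection duration, for example by partial Spearman correlation. This matters most if amount is chosen, because amount is the scale most sensitive to timing.
4. **Section 13.5:** pair exposure only with the end-of-intervention NQO1 change. No urine is collected at Visits 3 and 6 to match the Day 4–8 change.

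Do not move the start of collection to the evening meal. The same urine supplies the primary benzene endpoint and the nicotine measure (Sections 7.3 and 8.1), so an earlier start would change the primary specimen by adding waking, smoking hours.

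Cost: one form field and a little more analysis, with no extra visit or assay. A recorded gap allows adjustment but does not recover urine already missed. Dose times not written down at collection cannot be reliably reconstructed later, so the field should be added before further collections.

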10.3 Shipping Instructions

Collected frozen specimens will be placed on ice packs and hand delivered to the research laboratory for analysis.

10.4 Tissue Banking

Biologic specimens collected during the conduct of each clinical trial that are not used during the course of the study will be considered deliverables under the contract and thus the property of the NCI. At study completion, NCI reserves the option to either retain or relinquish ownership of the unused biologic specimens. If NCI retains ownership of specimens, the Contractor shall collect, verify and transfer the requested biologic specimens from the site to a NCI-specified repository or laboratory at NCI's expense.

11. **REPORTING ADVERSE EVENTS**

DEFINITION: AE means any untoward medical occurrence associated with the use of a drug in humans, whether or not considered drug related. An AE can therefore be any unfavorable and unintended sign), symptom, or disease temporally associated with participation in a study, whether or not related to that participation. This includes all deaths that occur while a participant is on a study. The participants in this study will use the symptom diary to record their AEs.

Please note that all abnormal clinical laboratory values that are determined to be of clinical significance based on a physician's assessment are to be reported as AEs. Those labs determined to be of no clinical significance or of unknown clinical significance (per the physician's assessment) should not be reported as AEs. Any lab value of unknown clinical significance should continue to be investigated/followed-up further for a final determination, if possible.

A list of AEs that have occurred or might occur can be found in §6.2 Reported Adverse Event AEs and Potential Risks, as well as the Investigator Brochure or package insert.

11.1 Adverse Events

11.1.1 Reportable AEs

All AEs that occur after the informed consent is signed and baseline assessments are completed (including run-in) must be recorded on the AE CRF (paper and/or electronic) whether or not related to study agent.

11.1.2 AE Data Elements:

The following data elements are required for AE reporting.

- AE verbatim term
- NCI Common Terminology Criteria for Adverse Events version 4.0 (CTCAE v4.0) AE term (MedDRA lowest level term)
- CTCAE (MedDRA) System Organ Class (SOC)
- Event onset date and event ended date
- Treatment assignment code (TAC) at time of AE onset
- Severity grade
- Attribution to study agent (relatedness)
- Whether or not the event was reported as a SAE
- Whether or not the subject dropped due to the event
- Outcome of the event

